The primary objective is to evaluate the median survival of patients with synchronous metastasized breast cancer and the primary tumor in place comparing arm A with local therapy to the primary tumor versus arm B without local therapy.

The secondary objectives are to evaluate time to distant and local progression as well as in pre-selected centers circulating tumor cells and growth factors in the peripheral blood within the two groups.

Studydesign

This study is a prospective, randomized, multicenter study concerning the influence of local treatment on patients with synchronous metastasized breast cancer. Patients will be stratified at inclusion according to the geographic region, the hormone-receptor status (ER-/PR-/not determinable; any PR and/or ER+), the HER-2 status (positive vs. negative/not determinable), the grading (G1/G2/not determinable vs. G3), location of metastases (visceral ± vs bone only) and use of first line therapy (anthracyclin-based ± any other, except taxan, vs. taxan-based ± any other vs. other therapies, e.g. antihormonal therapy alone). Thereafter patients will be randomly assigned to receive either local therapy of the breast (lumpectomy or mastectomy + axillary surgery /± radiotherapy) versus no local therapy. Surgery of the metastases is not allowed in both treatment regimens and may only be performed on demand. This will be considered as protocol deviation. Systemic therapy will be administered at the centers policy.

Treatment regimens

Therapy arm A, surgical therapy

Local therapy consists of lumpectomy or mastectomy with or without radiotherapy (according to center tumorboard decision) with a resection free margin of at least 1 mm or more demonstrated on paraffin embedded histological sections. Intraoperative frozen sections are allowed but not definitive for margin assessment. For axillary surgery, either axillary dissection level I and II or sentinel node biopsy has to be performed (mandatory) which has only to be followed by axillary dissection in case of macrometastasis of at least one sentinel lymph node..

Therapy arm B, surgery on demand

In arm B (no local therapy) it may be necessary to perform local therapy on demand (surgery, radiotherapy). Reasons may be uncontrolled bleeding or infected exulcerations with a septic component and no treatment benefit from conservative therapy. This will be considered as protocol deviation. However, the patient's follow up is recorded and data are available for analyses as intention to treat.

Radiation therapy

Local radiation therapy of the breast may be given according to center policy in therapy arm A. Radiation therapy of the metastases is allowed according to center policy in both arms.

Systemic therapy

Chemotherapy or anti-hormone therapy is used according to center policy. The following recommendations should be followed:

1. In cases of radiotherapy and chemotherapy (arm A), radiotherapy should not be given later than 6 months after surgery. Radiotherapy is allowed in parallel to anti-hormonal treatment.
2. In premenopausal patients anti-hormonal treatment - if indicated - should always be coupled with ovarian ablation (surgical resection or systemic endocrine treatment, e.g. with goserelin) to ensure complete hormonal blockade.
3. In postmenopausal patients the primary anti-hormonal treatment - if indicated - should be an aromatase inhibitor (if there are no contraindications).
4. Chemotherapy – if indicated – should precede anti-hormonal treatment – if indicated.

Number of patients

254 patients (127 in each group) including a drop out rate of 5%

Inclusion and exclusion criteria

Females whose conditions satisfy all of the following criteria are the only patients eligible for this study.

General inclusion criteria

1. Written informed consent must be obtained and documented prior to beginning any protocol specific procedures and according to local regulatory requirements.
2. Patients age \geq 18 years
3. Eastern Cooperative Oncology Group Performance Status is 0 -2 (Appendix 3)
4. Able to comply with the protocol requirements during the treatment and follow-up period.

Disease specific inclusion criteria

5. Untreated synchronous metastasized invasive carcinoma of the breast with the primary tumor in situ (bilateral synchronous metastasized breast cancer patients are eligible).
6. The primary tumor must be identified and may be any size, however, primary resection with resection free margins must be possible.
7. Invasive adenocarcinoma of the breast on histological examination.
8. The metastatic site must be identified by radiological assessment (Computer Tomography of the chest and the abdomen OR ultrasound and chest x ray for visceral metastases; bone scan AND/OR computer tomography AND/OR magnetic resonance for bone metastases). A biopsy is not necessary.

Exclusion criteria

1. Patients in whom a R0 resection (microscopic free margins) is clinically questionable
2. Inflammatory cancer
3. Patients with brain metastases
4. Patients who are not eligible for general anesthesia and operations
5. Patients without metastatic breast cancer (patients with a tumor marker value (CEA, CA15-3) above normal levels without the radiological proven evidence of metastases are not eligible for the study)
6. Patients with a second untreated malignancy
7. Any previous malignancy treated with curative intent and the patient has not been disease-free for 5 years – exceptions are:
 - a. carcinoma in situ of the cervix
 - b. squamous carcinoma of the skin
 - c. basal cell carcinoma of the skin
8. Patients with any recurrent cancer disease
9. Pregnant or lactating women
10. Patients are not allowed to be part of another local therapy trial

Stratification

- Geographic region
- Grading
 - G1/G2 **versus** G3/GX
- Receptor status
 - 0/0 **versus** any positive
- Her2neu status
 - FISH amplified/IHC+++ **versus** negative
- Location of metastases
 - visceral ± **versus** bone only
- Planned first line therapy
 - Anthracycline-based ± any other except taxane **versus** taxane-based ± any other **versus** any other therapy

Efficacy evaluation

Median survival

Time to local progression

Time to distant progression

Circulating tumor cells and growth factors in pre-selected centers

Quality of life

Timetable

Planned start date	Q1/10
Planned end enrollment date	Q1/14
Expected follow up end date	Q1/19

Introduction

Background and preliminary data

Overall survival for patients with metastasized breast cancer (stage IV) is limited. Most recent data report about a median survival between 11 and 23 months depending on prognostic factors and systemic therapy ¹⁻⁶. As cancer cells have already spread throughout the systemic circulation in stage IV breast cancer disease it is generally believed that systemic therapy may be the only life prolonging treatment. Even in stage I and II breast cancer patients more aggressive local therapy did not improve overall survival ^{7,8}.

Recently a meta-analysis by the Early Breast and Colorectal Trial Collaborative Group (EBCTCG) in 2002 updated in 2005 has shown that the prevention of local recurrence by local therapy significantly correlates with an improvement in overall survival in stage I and II breast cancer patients ⁹ suggesting an important role of local therapy for overall survival. The first clinical evidence that local therapy may be of benefit in stage IV disease arises from renal-cell cancer patients. Case reports about metastasis shrinkage after primary tumor resection in renal-cell cancer patients were followed by two randomized trials demonstrating that removal of the primary tumor in metastasized renal-cell cancer significantly improved survival ^{10,11}.

Regarding stage IV breast cancer patients Khan et al ⁴ evaluated 9162 patients accounting for 4.1% of all breast cancer patients entered into the National Cancer Data Base (NCDB) between 1990 and 1993. 43% had systemic treatment only while 57% underwent additional local surgery due to salvage treatment, patients wish or local complications. Local therapy consisted of partial or total mastectomy with or without axillary surgery. The use of radiotherapy has not been evaluated due to lack of data. Patients with surgical removal of the primary tumor had a significant increased 3-year survival rate (17% vs. 35%) with a hazard ratio of 0.61. Similar the Geneva Cancer Registry report from Rapiti et al ⁵ demonstrated a 40% reduced risk of death with the surgical removal of the primary tumor in 300 stage IV breast cancer patients. A significant improvement in progression free survival by this treatment has been demonstrated in 224 patients with stage IV breast cancer at the MD Anderson Cancer Center ¹ and Blanchard et al ² suggested a significant increase in median survival from 17 to 27 months for the surgical removal of the primary in 427 stage IV breast cancer patients at the Baylor College of Medicine. A retrospective analysis of the Surveillance, Epidemiology and End Results (SEER) program data of 9734 patients also demonstrated a 37% improvement for overall survival in patients with stage IV breast cancer and removal of the primary tumor ⁶. These data together strongly suggest an important role for local therapy in stage IV cancer disease. However, this has to be proven in prospective studies. More over the reason for a life extending role of local therapy in metastasized patients is unclear.

Theoretically there are some unproven speculative explanations. The primary tumor may act as a source for ongoing systemic spreading of chemoresistant cancer cells (circulating tumor cells, stem cells) ¹²⁻¹⁵ or metastases proliferation factors (TGFbeta ¹⁶⁻¹⁸, VEGF ¹⁹⁻²⁴) supporting systemic tumor growth and further metastases proliferation. Resection of the primary tumor may thus down regulate the constant release of circulating tumor cells/stem cells and/or proliferating factors ^{25,26} reducing the capacity to produce new metastases and decreasing proliferation of metastases.

The reduction of chemoresistant systemic stem cells by resection of the primary tumor may render metastatic cells chemosensitive. Clinically there is evidence that resection of the primary tumor may enhance the response to systemic therapy^{11,27,28}

Hypothesis

We first hypothesize that the removal of the primary tumor in stage IV breast cancer patients followed by systemic therapy improves median survival compared with no local therapy. In case that this main thesis proves true we secondly hypothesize that the ultimate reason for the improved survival by local therapy may be due to the reduction of stem cells or circulating proliferation factors such as VEGF or TGF beta in the peripheral system as these cells and factors may origin from the primary cancer. This may reduce metastatic growth kinetics and increase chemosensitivity of visceral and non-visceral metastases and prolong median and progression free survival.

Aim

The aim of the study is to investigate the effect of local therapy to the primary tumor in synchronous metastasized breast cancer patients and to evolve the role of circulating tumor cells and growth factors in the peripheral blood.

Study objectives

The primary study objective is

1. to demonstrate that the resection of the primary breast cancer in synchronous metastasized breast cancer patients increases the median survival.

The secondary study objectives are

1. to investigate the role of the primary breast cancer resection in terms of local and distant time to progression
2. to evaluate the role of peripheral circulating tumor cells and growth factors in synchronous metastasized breast cancer patients and whether there is any association between their detection and the median survival in pre-selected centers
3. to examine whether the resection of the primary breast cancer influences peripheral circulating tumor cells and growth factors in pre-selected centers
4. to investigate the quality of life in both groups

Patients

Sample Size Considerations

A sample of 254 patients will be enrolled in this trial (127 in each group) including a drop out rate of 5%. This assumes that there will be a 48-month accrual period. The median survival of patients with local therapy to the primary tumor should be increased by 50% in comparison to patients without local therapy to have 80% power to detect a hazard ratio of 0.666 with a two-sided significance level of 0.05. The recruitment period is assumed with 4 years. The maximum study duration should be 9 years.

Study design (Appendix 1)

This is a prospective multicenter national randomized study. Patients with a histological verified breast cancer are first screened for any metastatic disease. In cases of visceral or non visceral metastatic spreading (International Union against Cancer UICC M1 = stage IV; Appendix 2) the patient is eligible for the study taking into consideration all inclusion and exclusion criteria listed below. After signed informed consent the patient is randomized to either arm A (local treatment) or Arm B (no local treatment, only on demand). In arm A therapy consists of either breast conserving surgery or mastectomy. For axillary surgery, either axillary dissection level I and II or sentinel node biopsy has to be performed (mandatory) which has only to be followed by axillary dissection in case of macrometastasis of at least one sentinel lymph node, followed by radiotherapy (on centers preference). Surgery of the metastases is not allowed in both treatment arms and may only be performed on demand. This will be considered as protocol deviation. Systemic therapy follows surgery on the centers preference. In arm B only systemic therapy is given on the centers preference. Follow up should be done every 3 months during the first 2 years and from then on every 6 months and should include clinical, radiological and laboratory exams. The median survival is the primary endpoint, while the time to local or distant progression are defined as secondary endpoints.

Additional we measure circulating tumor cells and growth factors in the peripheral blood at pre-selected centers. Therefore 15ml of blood are drawn before surgery and 1-3 days after surgery (arm A only), as well as before first application of systemic therapy, 3-6 months and 12 months after first application of systemic therapy in both arms.

Quality of life questionnaires are handed out to all patients before surgery or first application of systemic therapy as well as every 6 months after enrollment until 42 months visit.

Inclusion and Exclusion Criteria

Females whose conditions satisfy all of the following criteria are the only patients eligible for this study.

General inclusion criteria

1. Written informed consent must be obtained and documented prior to beginning any protocol specific procedures and according to local regulatory requirements.
2. Patients age ≥ 18 years
3. Eastern Cooperative Oncology Group Performance Status is 0 -2 (Appendix 3)
4. Able to comply with the protocol requirements during the treatment and follow-up period.

Disease specific inclusion criteria

5. Untreated synchronous metastasized invasive carcinoma of the breast with the primary tumor in situ (bilateral synchronous metastasized breast cancer patients are eligible).

6. The primary tumor must be identified and may be any size, however, primary resection with resection free margins must be possible.
7. Invasive adenocarcinoma of the breast on histological examination.
8. The metastatic site must be identified by radiological assessment (Computer Tomography of the chest and the abdomen OR ultrasound and chest x ray for visceral metastases; bone scan AND/OR computer tomography AND/OR magnetic resonance for bone metastases). A biopsy is not necessary.

Exclusion criteria

1. Patients in whom a R0 resection (microscopic free margins) is clinically questionable
2. Inflammatory cancer
3. Patients with brain metastases
4. Patients who are not eligible for general anesthesia and operations
5. Patients without metastatic breast cancer (patients with a tumor marker value (CEA, CA15-3) above normal levels without the radiological proven evidence of metastases are not eligible for the study)
6. Patients with a second untreated malignancy
7. Any previous malignancy treated with curative intent and the patient has not been disease-free for 5 years – exceptions are:
 - a. carcinoma in situ of the cervix
 - b. squamous carcinoma of the skin
 - c. basal cell carcinoma of the skin

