2. In premenopausal patients anti-hormonal treatment - if indicated - should always be coupled with ovarian ablation (surgical resection or systemic endocrine treatment, e.g. with goserelin) to ensure complete hormonal blockade.

3. In postmenopausal patients the primary anti-hormonal treatment - if indicated - should be an aromatase inhibitor (if there are no contraindications).
4. Chemotherapy – if indicated - should precede anti-hormonal treatment – if indicated.

Follow up (Appendix 4)

Routine laboratory tests for safety assessment of palliative systemic therapy and radiological follow up are performed according to the centers' guidelines with the recommended procedures as follows:

- Clinical examination and laboratory tests (red and white blood cells, Tumor marker CA15-3 and CEA) before and every 2-4 months after randomization. After two years examinations should be done every 5-7 months.
- CT scan of the liver and the lung before and every 2-4 months after randomization. Alternatively a PET-CT scan can be performed. Ultrasound of the liver or chest X-ray is only recommended in cases of contraindication for CT. After two years examinations should be done every 5-7 months.
- CT scan or alternatively PET-CT scan of bone metastases (if diagnosed) before and in case of pre-randomization diagnosed bone metastases every 2-4 months after randomization or in case of suspect new bone metastases anytime after randomisation for diagnostic imaging. After two years examinations should be done every 5-7 months.
- EORTC QLQ-C30 and QLQ-BR23 quality of life (Appendix 5) sheets before and every 6 months after treatment until 24 months visit, then every 12 months until 48 months visit.

Blood specimens in pre-selected centers (Appendix 6)

15ml of blood are drawn before surgery and 1-3 days after surgery (arm A only), as well as before first application of systemic therapy, 3-6 months and 12 months after first application of systemic therapy in arm A and arm B.

Tissue specimens in pre-selected centers

Tumor tissue from core needle biopsies before systemic therapy (arm B no local therapy group) or from surgical resections (arm A local therapy group) are used for further immunhistochemical and flow cytometry analyses. Only in pre-selected centers with experimental background.

Measurements of VEGF and TGF beta in pre-selected centers

Blood

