3.6.3. Efficacy analyses for secondary endpoints

Difference in time to distant progression and time to local progression between local therapy versus no local therapy will be estimated through 2-sided log-rank

With respect to analysis of QoL endpoints the mean change of the linear transformed scores from baseline (and 95% CI using the normal approximation) will also be assessed. Line charts depicting the mean changes (and standard errors) of items and subscales over time will be provided for each treatment arm from the baseline assessment.

Completion and compliance rates will be summarized at each time point by treatment arm with reasons for missing data.

Reduction of growth factors, circulating tumor cells, stem cells in pre-selected centers will be defined in later version of SAP in an efficient amount of data will be available.

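### The first quality-of-life form is timed to treatment and not to randomisation, so a baseline completed after the patient knows her arm is permitted and would distort the change-from-baseline summaries

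*Protocol*

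**What the plan says.** The protocol times the first EORTC form in two places. Study design states that "Quality of life questionnaires are handed out to all patients before surgery or first application of systemic therapy". The Follow up section lists "EORTC QLQ-C30 and QLQ-BR23 quality of life (Appendix 5) sheets before and every 6 months after treatment until 24 months visit". Both tie the form to treatment, and neither mentions randomisation as its limit.

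The order of events is in Study design: "After signed informed consent the patient is randomized to either arm A (local treatment) or Arm B". For arm A, "Systemic therapy follows surgery on the centers preference"; arm B receives systemic therapy alone. Allocation therefore comes before either treatment.

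Other entries in the same Follow up list are anchored differently, for example "CT scan of the liver and the lung before and every 2-4 months after randomization". Clinical examination and laboratory tests are also timed against randomisation. The whole list is introduced as recommended procedures.

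Nothing elsewhere settles the timing. The Appendix 4 chart begins at month 3 and has no baseline column. SAP 3.3.2, 3.6.2 and 3.6.3 use the term baseline for quality of life without saying when it is taken. SAP 3.6.1 makes the questionnaire scores the endpoints, and SAP 3.6.3 adds "the mean change of the linear transformed scores from baseline" with a normal-approximation 95% CI, plus line charts of mean change for each arm. No baseline-adjusted quality-of-life model is specified, the covariate list in SAP 3.9 has no baseline quality-of-life score, and SAP section 4 lists no quality-of-life table or test.

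**The concern.** A baseline is meant to be a measurement that the allocation cannot have influenced. No blinding is described, and none is feasible for surgery against no surgery. Between allocation and treatment, a patient in arm A knows that she faces an operation and a patient in arm B knows that she does not.

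The forms in Appendix 5 contain items that could plausibly respond to that knowledge: tension and worry (items 21 and 22), overall health and quality of life (29 and 30), body image (39 to 42) and worry about future health (43). These items ask about the past week, so a form completed some days after allocation may cover time when the arm was already known.

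If the reaction differs between arms, the baseline difference becomes a spurious difference in change. Quality of life in both groups is a stated secondary objective, and charts of change by arm will be read as a comparison even without a formal test.

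**Working it through.** **Is a post-allocation baseline allowed?** The sequence is consent, randomisation, then surgery (arm A) or systemic therapy (arm B). The form is due before treatment. Any time from consent up to treatment satisfies that, including the interval after randomisation. Nothing in Appendix 4 or the SAP narrows it, so the timing is permitted but not mandated.

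**Effect on change scores.** Let d be the shift in mean baseline in arm A minus that in arm B caused by knowing the arm, with no true effect on follow-up scores.

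- Difference in mean change = (follow-up A − follow-up B) − (baseline A − baseline B) = 0 − d = −d.
- This holds at every visit, whatever the correlation between baseline and follow-up.
- With baseline as a covariate and equal SDs, the slope is the correlation r, so the adjusted difference is 0 − r × d. At r = 0.5, half of d remains.
- The raw follow-up scores do not involve baseline and carry no bias from this source.

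**Simulation check** (4000 runs per setting, 127 per arm as in the protocol, no true effect, shift in one arm only, SD units; shifts and correlations are assumed):

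| Shift | r | Bias in difference in change | Bias after baseline adjustment | 95% CI for the difference excludes 0 |
|---|---|---|---|---|
| 0 | 0.4 / 0.6 / 0.8 | about 0 | about 0 | 5.8% / 5.1% / 4.9% |
| 0.1 | 0.4 / 0.6 / 0.8 | about −0.10 | −0.04 / −0.06 / −0.08 | 12% / 14% / 24% |
| 0.2 | 0.4 / 0.6 / 0.8 | about −0.20 | −0.08 / −0.12 / −0.16 | 30% / 44% / 70% |

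The zero-shift row is the situation with a form completed before randomisation.

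**Scale in points** (assumed: SD 20 to 25, r = 0.5, 100 patients per arm at month 6; the documents give none of these). SD of change = SD × √(2(1 − 0.5)) = SD.

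- Within one arm, SE of mean change = SD/√100 = 2.0 to 2.5, so the 95% half-width is 1.96 × 2.0 = 3.9 to 1.96 × 2.5 = 4.9. A 5-point shift confined to one arm would exceed the half-width of that arm's own interval.
- Between arms, SE = SD × √(2/100) = 2.8 to 3.5. If a reader formed a 95% CI for the difference, it would exclude zero with probability P(|Z| > 1.96), Z ~ N(d/SE, 1): 14–19% for d = 3, 29–42% for d = 5 and 62–81% for d = 8, against 5% with no shift.

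The plan states no quality-of-life SD, margin or power, so there is no figure of its own to reproduce.

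**The case against.** The wording sets a latest time and is silent on the earliest, so a centre that collects the form at the consent visit is fully compliant. A reader might infer that the protocol directs collection after allocation. It does not.

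A reader might also infer that each arm has its own trigger, surgery in A and systemic therapy in B. The sentence refers to all patients and can be read as before whichever treatment comes first. The arm-specific reading arises only by combining it with the treatment sequence. Likewise, the examinations, laboratory tests and CT timed to randomisation are recommended and not required. The difference in wording is real, but it is not a contrast between a strict rule and a loose one.

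The percentages above describe a between-arm interval that SAP 3.6.3 does not plan. Change is also not the only quantity: the scores themselves are endpoints and are not contaminated, although the SAP does not say how they would be compared. Finally, nothing in the documents shows that a shift occurs. Its sign is open too, since distress at not having the tumour removed could lower arm B's baseline as readily as anticipation of surgery could lower arm A's.

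All of this stands, and it limits the point. It does not remove it: the permitted timing is inferior to an equally easy alternative, and the change summaries that are planned would absorb any shift in full.

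**Conclusion.** The plan permits a quality-of-life baseline taken after an allocation that the patient knows, and no passage closes the gap. Any differential shift d enters the between-arm contrast in mean change as −d. Baseline adjustment would reduce it only to about −r × d.

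The algebra needs no assumption about SD or correlation, but whether d differs from zero, how large it is and which arm it would favour cannot be derived from the documents. The 14–81% range should not be read as the error rate of this trial: it rests on assumed inputs and on a comparison that the SAP does not specify.

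The effect is confined to change scores for one secondary objective. Follow-up scores and the survival and progression analyses are untouched. This is a worthwhile, low-cost improvement to the design and does not threaten the trial's main conclusion.

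**What to change.** **Protocol, Study design and Follow up.** Change only the baseline clause in each, so that the EORTC QLQ-C30 and QLQ-BR23 are completed *after informed consent and before randomisation in both arms*. Keep the follow-up schedule, but reconcile it while these sentences are open. Study design counts from enrolment, every 6 months to month 42. Follow up counts from treatment, every 6 months to month 24 and then yearly to month 48. The Appendix 4 chart appears to run to month 60.

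**SAP 3.6.** Define the quality-of-life baseline as the last form completed before randomisation. For patients already enrolled, compare form dates with randomisation dates, flag forms completed later, and show change scores with and without them. Also show follow-up scores by arm, since these do not depend on the baseline. If nearly all forms post-date randomisation, the with/without comparison will say little and the follow-up scores become the main safeguard.

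**Cost.** One clause in each of two protocol sections and a short SAP paragraph. The instrument and the number of assessments stay the same. A few consented patients who are never randomised will also complete a form.
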